### 4. STUDY DESIGN

### 4.1. Overall Study Design

AFM24-102 is a Phase 1/2a open-label, non-randomized, multicenter, dose escalation and expansion study evaluating AFM24 in combination with atezolizumab (investigational treatment: AFM24 + atezolizumab) in patients with select *EGFR*-expressing advanced solid malignancies whose disease has progressed after treatment with previous anticancer therapies.

There will be 2 parts in this study: a dose escalation phase (Phase 1) and an expansion phase (Phase 2a). Patients will qualify to receive the investigational treatment (AFM24 + atezolizumab) in the dose escalation phase (Phase 1) or in the expansion phase (Phase 2a) only if they are deemed eligible post the safety lead-in phase where they will receive a single i.v. AFM24 infusion (see Section 4.2.2). Patients who qualify the safety-lead in phase will receive AFM24 i.v. infusion, qw, in 4-week cycles and atezolizumab i.v. infusion, q2w, in 4-week cycles.

Overall, the study will consist of following periods:

- Pre-Screening period
- Screening period ( $\leq 21$  days prior to Day -7)
- Safety lead-in phase (Day -7 through Day -1) to evaluate patient's hypersensitivity to AFM24 *only* infusion

**Note:** Some of the screening assessments will be allowed during the safety lead-in phase as well. Please review the Inclusion Criteria (Section 5.1) and Exclusion Criteria (Section 5.2) to see allowed time periods of screening assessments.

- Treatment Period (AFM24 + atezolizumab)
  - o Dose Escalation Phase (Phase 1)
  - o Expansion Phase (Phase 2a)

**Note**: Patients will receive the investigational treatment (AFM24 + atezolizumab) until disease progression, intolerable toxicity, Investigator discretion, or patient withdrawal of consent.

- Follow-Up
  - End of Treatment (EOT) Visit (14 days [±2 days] after the last administration of AFM24 or before start of any new anti-cancer treatment whichever is sooner)
  - O Safety Follow-Up Visit (30 days [±5 days] after the last administration of study treatment or before start of any new anti-cancer treatment whichever is sooner)
  - Long-term follow-up (patients will be contacted every 3 months [±2 weeks] to collect data on their subsequent therapies and disease status.

**Note**: Patients who are permanently discontinued from the study during the safety lead-in phase should complete the EOT visit and the Safety follow-up visit but will not be required to complete the long-term follow up.

# 4.2. Overall Study Periods

## 4.2.1. Pre-Screening and Screening

## **Pre-Screening:**

Pre-Screening is required for all patients planned to be enrolled in this trial. EGFR expression is to be assessed for EXP-2 and EXP-3 cohorts as per Inclusion Criterion #4 before the patient enters the screening phase. Archived paraffin embedded tumor tissue is acceptable for EGFR determination otherwise, a fresh tumor biopsy must be performed. EGFR assessment by a locally validated immunohistochemistry assay test is acceptable.

Patients will sign a Pre-screening informed consent form (ICF) allowing the testing of EGFR expression to determine whether eligibility criteria for EGFR expression have been met prior to entering Screening (**Note**: if a positive EGFR test has been performed from a patient's tumor tissue, and the EGFR laboratory report is available, the patient does not have to sign the pre-screening ICF and perform the pre-screening assessment and can directly proceed to signing the Main ICF and the screening activities).

The Screening phase starts only after the patient has met the eligibility criterion for EGFR expression for EXP-2 and EXP-3 cohorts, and has signed the main ICF for all cohorts.

## **Screening:**

The screening period lasts up to 21 days prior to the safety lead-in phase (from Day -7 through Day -1). The screening period begins when the main ICF is signed and ends on the day before the first dose of AFM24 infusion on Day -7. Before entering the study, all study procedures and possible risks will be explained to each patient who is asked to participate in the study. After provision of main written informed consent for the study, screening assessments will include a careful review of the patient's medical history, assessment of Eastern Cooperative Oncology Group (ECOG) performance status (PS), physical examination, electrocardiogram (ECG), laboratory assessments, and tumor assessments by computed tomography (CT) or magnetic resonance imaging (MRI), and tumor histopathology. Screening assessments are to be performed within 21 days of the first dose of AFM24 infusion (i.e., on Day -7); however, radiographic tumor assessment is allowed up to 28 days prior to first dose of AFM24 infusion (i.e., on Day -7). Patients who do not meet 1 or more eligibility criteria may be re-screened. Patient's eligibility criteria must be re-confirmed on or within 7 days before Day -7, before administration of the first AFM24 infusion. The assessments for hepatitis B, hepatitis C, and human immunodeficiency virus (HIV) do not need to be repeated for re-screened patients if performed within 3 months before the first AFM24 infusion (i.e., on Day -7). Please review the inclusion (Section 5.1) and exclusion criteria (Section 5.2) to see allowed time periods of screening assessments.

# 4.2.2. Safety Lead-In Phase (for Both the Dose Escalation Phase [Phase 1] and the Expansion Phase [Phase 2a])

Seven days prior to Cycle 1 Day 1 (C1D1) (i.e., at Day -7), patients will receive a single dose of AFM24 (dose assigned to a given cohort) and will be observed for any AE for 1 week (from Day -7 through Day -1, the safety lead-in phase). Patients who have any Grade ≥3 cytokine release syndrome (CRS) or IRR symptoms lasting >6 hrs or any other possibly treatment-related Grade ≥3 non-hematological TEAEs or clinically significant hematological Grade ≥3 TEAEs during their

. Patient's eligibility criteria must be re-confirmed on or within 7 days before Day -7, before the administration of the first AFM24 infusion; please refer to inclusion and exclusion criteria sections (Sections 5.1 and 5.2, respectively) to see allowed time periods of screening assessments.

Patients not proceeding to combination therapy (AFM24 + atezolizumab) will be replaced.

Note: Patients are required to receive premedication approximately 1 hour before each dose of AFM24; a list of premedications is provided in Section 6.3.

#### 4.2.3. Dose Escalation Phase (Phase 1) Study Design

The aim of the dose escalation phase (Phase 1) is to determine the MTD/RP2D of AFM24 in combination with atezolizumab.

The 160 mg i.v. qw dose was selected as the starting dose for the AFM24-102 study, based on the data obtained from the FIH study (AFM24-101) ( ). There are additional dose escalations planned for AFM24, where the dose increase will be based on data from AFM24-101 in conjunction with the safety and PK data emerging from this study ( ). Dose increases will not exceed 200% of the current dose. All dose escalation (and de-escalation) decisions will be determined by the SRC.

It is estimated that approximately 18 patients will be treated in Phase 1 of the study. The number of patients is dependent on the tested dose cohorts and safety profile of AFM24 in combination with atezolizumab.

#### **Dose cohorts**

Patients will be enrolled sequentially in cohorts of 3 to 6 patients into dose escalation phase (Phase 1). The dose escalation will follow 3+3 dose escalation design. In each cohort there will be at least 3 patients enrolled. The first 2 patients of each dose cohort will begin treatment in a staggered approach with at least 7 days between first dosing of these 2 patients. Subsequent patients may be enrolled concurrently. All patients who start treatment need to complete the 28-day DLT observation period or experience a DLT within the first cycle of treatment to be DLT evaluable. A minimum of 3 patients needs to be DLT evaluable per dose cohort. If no DLT is observed, the dose is escalated for the next cohort of 3 patients. If 1 DLT is observed, 3 additional patients will be treated at this dose level with dose escalation only if no additional DLTs occur. If less than 3 patients are evaluable for DLT assessment, replacement patient(s) will be enrolled. DLTs will be assessed in the first treatment cycle (i.e., the first 4 weeks of treatment for each patient, starting C1D1), referred to as the DLT observation period (28-days). Dose limiting toxicity will be defined by the criteria listed in Section 4.2.3.1. The number of patients included in each dose cohort may be increased from 3 up to 6 patients based on SRC decision to allow for further collection of safety, pharmacodynamic and PK data.

A 3+3 design will be used to determine the RP2D, with the schematic escalation rules given below. The number of patients with DLT at a given dose level will be evaluated as:

- 1. If 0 out of 3
  - Escalate to next higher dose level

#### 2. If 1 out of 3

- Enter 3 more patients at this dose level:
  - o If 0 of these additional patients experience a DLT, proceed to the next higher dose level
  - o If 1 or more of these additional patients experience a DLT, the dose escalation will be stopped. Up to 3 additional patients will be entered at the lower dose level if only 3 patients were treated previously at that dose level. Alternatively, up to 6 additional patients could be entered to receive intermediate dose levels, based on the emerging safety, PK, and pharmacodynamic data observed in the FIH AFM24-101 study If this occurs in Cohort 1, there will be a de-escalation to Cohort -1.

#### 3. > 2 out of 3

• Dose escalation will be stopped. Up to 3 additional patients will be entered at the lower dose level if only 3 patients were treated previously at that dose level. Alternatively, up to 6 additional patients could be entered to receive intermediate dose levels, based on the emerging safety, PK, and pharmacodynamic data observed in the FIH AFM24-101 study. If this occurs in Cohort 1, there will be a de-escalation to Cohort -1.

## **4.2.3.1.** Definition of Dose-Limiting Toxicity (DLT)

DLT is defined as an AE or abnormal laboratory value assessed as unrelated to underlying disease, disease progression, inter-current illness, or concomitant medications, that occurs ≤28 days following the first dose of AFM24 in combination with atezolizumab (Cycle 1) and that meets any of the following criteria shown in Table 1. Clinically relevant toxicities will be evaluated according to the National Cancer Institute (NCI)/National Institutes of Health (NIH) Common Terminology Criteria for Adverse Events (CTCAE) v5.0. Patients who experience a DLT during Cycle 1 must permanently discontinue AFM24 and atezolizumab.

## **DLT** observation period:

In order to be considered evaluable for DLT, patients must meet the following criteria:

- receive  $\geq 75\%$  of their assigned AFM24 dose in Cycle 1 *and*
- receive  $\geq 50\%$  of their assigned atezolizumab dose in Cycle 1 and
- either complete the 28-day DLT observation period *or* have had a DLT within the first cycle of treatment.

Patients discontinuing the study after the safety lead-in phase will not be included in the DLT evaluation.

**Table 1:** Definition of Dose-Limiting Toxicity

Toxicity	Any of the following criteria		
Hematological a	≥CTCAE Grade 4 neutropenia (ANC<0.5×10  /L) lasting for longer than 4 consecutive day		
	Febrile neutropenia (ANC<1.0×10  /L of any duration accompanied by fever ≥38.5°C or systemic infection) that does not resolve within 48 hours after start of antibiotics		
	CTCAE Grade 3 thrombocytopenia (platelets 25 to <50×10  /L) associated with bleeding		
	CTCAE Grade 4 thrombocytopenia (platelets <25×10  /L)		
	≥CTCAE Grade 4 anemia that is considered to be treatment related		
Non- hematological	
 
Any ≥CTCAE Grade 3 AE including, but not limited to:
 
CTCAE Grade 3 infusion-related reaction/cytokine release syndrome not responsive to symptomatic treatment within 6 hours (i.e., no improvement to Grade 2 or better within 6 hours with optimal medical management)
 
CTCAE Grade 4 infusion-related reaction/cytokine release syndrome
 
QTcF prolongation (>500 msec) confirmed by 2 separate ECGs at least 6 hours apart or if associated with arrhythmias;
 
CTCAE Grade 3 hypertension for >14 consecutive days despite optimal antihypertension therapy;
 
CTCAE Grade 4 hypertension (any duration)
 
≥CTCAE Grade 3 total bilirubin (>3×ULN);
 
≥CTCAE Grade 3 ALT, AST, or alkaline phosphatase (>5×ULN) if not resolving to Grade 1 or baseline within 10 days;
 
≥CTCAE Grade 3 diarrhea for ≥72 hours despite optimal anti-diarrhea treatment
 
Any death at least possibly related to any study treatment
 
		
	Any other ≥CTCAE Grade 3 AE not listed above, except for the exceptions noted below		
Exceptions to DLT criteriab	Isolated laboratory changes of any grade without clinical sequelae or clinical significance except for those laboratory changes outlined above		
	CTCAE Grade 3 fever (in the absence of neutropenia) or fatigue that resolves to <grade 3="" 72="" hours<="" td="" within=""></grade>		
	CTCAE Grade 3 hypertension for ≤14 consecutive days		
	CTCAE Grade 3 nausea, vomiting, diarrhea, or dehydration that resolves to <grade 3="" 72="" care="" hours="" initiating="" of="" optimal="" supportive="" td="" treatment<="" within=""></grade>		
	CTCAE Grade 3 infusion-related reaction/cytokine release syndrome responsive to symptomatic treatment within 6 hours (i.e., improvement to Grade 2 or better within 6 hours with optimal medical management)		

Abbreviations: AE = adverse event; ALT = alanine aminotransferase; ALP = alkaline phosphatase; ANC = absolute neutrophil count; AST = aspartate aminotransferase; CRS = cytokine release syndrome; CTCAE = Common Terminology Criteria for Adverse Events; DLT = dose-limiting toxicity; ECG = electrocardiogram; IRR = infusion-related reaction; NCI = National Cancer Institute; QTcF = corrected QT interval by Fridericia; SRC = Safety Review Committee; ULN = upper limit of normal

- a. Patients may receive supportive care (e.g., use of granulocyte-colony stimulating factor, packed red blood cells, and platelets) as per local institutional guidelines. However, during the DLT observation period, it is not allowed to administer these supportive measures without clinical indication.
- The SRC (in Phase 1) and IDMC (in Phase 2) will closely monitor and review all AEs including the incidences of the AEs listed under the "Exceptions to DLT criteria" during the scheduled and any ad-hoc SRC/IDMC meetings.
   Note: NCI CTCAE v5.0 will be used for all grading.

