#### 9.1. Population for Analyses

For the purposes of analysis, the following populations are defined:

The **safety analysis set (SAS)** will consist of all patients who received at least any amount of AFM24 or atezolizumab. The SAS set will be the primary population for all safety related endpoints except determination of the dose-DLT relationship.

The **full analysis set (FAS)** will consist of all patients who received at least any amount of both, AFM24 and atezolizumab. The FAS will be the primary population for all efficacy related endpoints.

The **dose-determining set (DDS)** will consist of all patients in the safety set, who have either (a) experienced DLT at any time during Cycle 1, or (b) met the minimum safety evaluation requirements without experiencing DLT within Cycle 1.

Additional details of DLT observation period and criteria to determine patients available for DLT are described in Section 4.2.3.1.

The DDS will be used in the escalation phase (3+3 design) to estimate the dose-DLT relationship.

The **PK** set consists of all patients who have received at least one adequately documented dose of AFM24 and have at least one adequately documented post dose PK measurement.

Patients who are screened and sign the informed consent but do not receive any treatment will be listed including reason for screening failure and any SAE that is related to study procedure. These patients will not be part of any summary table except for summarizing disposition.

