# 7.3 Dose-Determining Set (DDS)

The DDS will consist of all patients in the Safety Analysis Set, who have either (a) experienced DLT at any time during Cycle 1, or (b) met the minimum safety evaluation requirements without experiencing DLT within Cycle 1.

Patients must receive ≥ 75% of their assigned AFM24 dose in Cycle 1, receive ≥ 50% of their assigned atezolizumab dose in Cycle 1, complete the 28-day DLT observation period and have at least one post-baseline assessment of the following safety parameters: Physical Examination, Vital Signs, Laboratory, and Electrocardiogram (ECG), or have had a DLT within the first cycle of treatment to be considered evaluable for DLT.

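### The DLT evaluability list in Protocol 4.2.3.1 contradicts Protocol 4.2.3, Protocol 9.1 and SAP 7.3: read literally, a DLT before the Day 15 AFM24 dose would not be evaluable

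*Protocol*

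**What the plan says.** Protocol 4.2.3.1, under the DLT observation period, introduces its list with "In order to be considered evaluable for DLT, patients must meet the following criteria". Three items follow:

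- at least 75% "of their assigned AFM24 dose in Cycle 1", linked to the next item by 'and';
- at least half of the atezolizumab planned for that cycle, again linked by 'and';
- as the third item, a choice: "either complete the 28-day DLT observation period *or* have had a DLT within the first cycle of treatment".

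The opening part of the same section adds: "Patients who experience a DLT during Cycle 1 must permanently discontinue AFM24 and atezolizumab".

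Other places state a different rule:

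- Protocol 4.2.3 (Dose cohorts) makes a patient evaluable on finishing the 28 days or on having a DLT, with no dose minimum.
- Protocol 9.1 puts in the DDS every patient who "experienced DLT at any time during Cycle 1". It applies minimum requirements only to patients without a DLT, and names the DDS as the set for the 3+3 escalation.
- SAP 7.3 repeats that definition, lists the dose, completion and assessment requirements, and ends with the alternative "or have had a DLT within the first cycle of treatment to be considered evaluable for DLT".

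Protocol 9.1 also sends the reader to 4.2.3.1 for the evaluability criteria. Protocol 5.6 takes its DLT requirements from 4.2.3.1 as well, and replaces only patients who stop for a reason other than a DLT.

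**The concern.** The alternative "have had a DLT within the first cycle of treatment" sits inside the third item only. It excuses a patient from completing 28 days but not from the dose minima. Because a DLT ends treatment, a patient whose DLT comes early cannot go on to reach 75% of the AFM24 dose. Under this list the patients with the earliest toxicity would leave both numerator and denominator of the DLT rate.

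The rule sits behind the Phase 1 primary endpoint. The MTD needs fewer than 2 of 6 patients with a DLT and a rate below 0.33. The RP2D needs a rate below 0.33 with at least 6 patients treated (Protocol 4.2.3.2 and 4.2.3.3). The RP2D chosen here, 480 mg, is the dose for all four expansion cohorts, up to 130 patients.

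The sections also leave open what happens to such a patient. Under 4.2.3.1 the patient is not evaluable. Under 5.6 the patient is not replaced, since the reason for stopping is a DLT. Under 4.2.3 a replacement is enrolled whenever fewer than 3 patients are evaluable.

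**Working it through.** **The plan's own figures.** Protocol 9.1.1 gives 3 cohorts × 6 = 18 patients, based on the DDS; this reproduces. The two forms of the tolerability rule agree: 1/6 = 0.167 is below 0.33, and 2/6 = 0.333 is not.

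**Dose received by the time of a DLT.** Protocol 6.2 gives AFM24 weekly (Cycle 1 Days 1, 8, 15, 22) and atezolizumab every 2 weeks (Days 1, 15). Assuming complete infusions on schedule:

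| Last dosing day before the DLT | AFM24 | Atezolizumab | Both minima met? |
|---|---|---|---|
| Day 1 | 1/4 = 25% | 1/2 = 50% | No |
| Day 8 | 2/4 = 50% | 1/2 = 50% | No |
| Day 15 | 3/4 = 75% | 2/2 = 100% | Yes |
| Day 22 | 4/4 = 100% | 2/2 = 100% | Yes |

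The AFM24 minimum is the one that fails. If the Day -7 lead-in dose were counted as a fifth dose, the shares after Days 1 and 8 would be 2/5 = 40% and 3/5 = 60%, still below 75%. So a DLT on Days 1–14 fails the 4.2.3.1 list, while Protocol 4.2.3, Protocol 9.1 and SAP 7.3 all count it.

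**What one patient can do (hypothetical).** Take 6 treated patients, two with a DLT, one of them before Day 15. Under the DDS the rate is 2/6 = 0.333, which is not below 0.33. Under 4.2.3.1 it is 1/5 = 0.20, or 1/6 = 0.167 if the early patient is replaced by one without a DLT. Both are below 0.33.

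**Illustration of the direction of error.** Let p be the true DLT rate and f the share of DLTs before the Day 15 dose. If those patients are dropped and replaced, the rate seen is

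e = p(1 − f)/(1 − pf).

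The 3+3 rule escalates on 0/3, or on 1/3 followed by 0/3:

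P(escalate) = (1 − e)³ + 3e(1 − e)⁵.

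At p = 0.33:

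- f = 0: e = 0.33, and 0.67³ + 3 × 0.33 × 0.67⁵ = 0.301 + 0.134 = 0.434 (rounded)
- f = 0.25: e = 0.2475/0.9175 = 0.270, P = 0.557
- f = 0.50: e = 0.165/0.835 = 0.198, P = 0.714
- f = 0.75: e = 0.0825/0.7525 = 0.110, P = 0.890

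The documents give no value for f, so the range 25–75% is an assumption. Under the DDS definition nothing is dropped and P stays at 0.434.

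**The case against.** The strongest reply is that one list is out of step and everything else is right. The DDS is the named escalation set, the basis of the Phase 1 sample size and the set for the primary endpoint. It admits any Cycle 1 DLT whatever dose was received. Protocol 4.2.3, where the escalation rules stand, agrees, and so does SAP 7.3. A reader might infer from 4.2.3.1 that early DLTs do drop out of the MTD/RP2D decision. The documents do not support that, and this part of the reply stands.

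A reader might also infer that early DLTs must be common, because infusion reactions cluster at the start of treatment. That does not follow either. Protocol 10.3.3.2 ties most of these reactions to the first infusion, which is the Day -7 lead-in, before the DLT window opens on Cycle 1 Day 1. Nothing in the documents favours a particular early share.

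The escalation probabilities also assume replacement, which Protocol 5.6 does not grant to a patient who stops for a DLT. They show direction and possible scale, not an estimate.

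A DLT would be hard to lose from view. Protocol 10.1.2 makes each one an SAE, Protocol 9.3.1 lists all events meeting the criteria, and the Safety Review Committee (SRC) decides each escalation. Phase 1 is also finished: SAP 4.4 reports that the RP2D was determined and the MTD not reached, so rewording cannot alter an escalation.

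The contradiction itself remains. The discordant list is the one that 9.1 and 5.6 cite as the source. Visibility of an event as an SAE also does not settle whether the patient counted in the DLT rate.

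**Conclusion.** The contradiction is real and should be reconciled. Read literally and combined with mandatory discontinuation, Protocol 4.2.3.1 makes a patient with a DLT before the Day 15 AFM24 dose non-evaluable. Protocol 4.2.3, Protocol 9.1 and SAP 7.3 count that patient. If 4.2.3.1 were followed, the error would run towards declaring a dose tolerable. Its size cannot be determined from the documents; the illustrative probabilities hold only for the assumed DLT rate, early share and replacement.

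There is no evidence that any DLT was set aside. Nor do the documents show which rule the SRC applied. The SAP supplied is a draft of 22 July 2024 that describes the escalation decisions as already made. Protocol 6.6 in version 4.0 already names 480 mg as the RP2D, so the decisions may have been taken under a version not supplied. SAP 4.6.1 lists 4 patients at 160 mg and 6 at 480 mg. No reason is given for the 4, and this proves nothing. Six is exactly the number treated that an RP2D requires, so the result would turn on whether one or two patients had a DLT. That is enough to justify a check after the fact.

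**What to change.** Reword the list in Protocol 4.2.3.1 to agree with Protocol 4.2.3, Protocol 9.1 and SAP 7.3. A patient is evaluable if there was a DLT in Cycle 1, whatever share of the dose was received. A patient without a DLT is evaluable if at least 75% of the AFM24 dose and at least 50% of the atezolizumab dose were received and the 28 days were completed. The references from 9.1 and 5.6 then point to a consistent rule, and SAP 7.3 needs no change on this point.

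In the clinical study report, state that no Cycle 1 DLT among the 4 + 6 = 10 patients at 160 mg and 480 mg was treated as non-evaluable or replaced, or give the recount if one was. SAP 4.3 speaks of two further escalation steps, so if any other cohort was treated it belongs in the check.

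The cost is one reworded list and a review of 10 patient records. The events are already collected as SAEs and listed, so no new data or analysis are needed. Restoring an omitted DLT could only raise the reported DLT count.
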